ST2	Suppressor of tumorigenicity 2
TID	Ter in die (three times a day)

Study Summary

Title	A Phase II, Open Label Prospective Single Center Drug Study Evaluating the Safety and Efficacy of (+)-Epicatechin in Subjects with Friedreich’s Ataxia
Running Title	Safety and Efficacy of (+)-Epicatechin in Friedreich’s Ataxia
Protocol Number	15-006845
Phase	Phase II
Methodology	This is an open label, single center, prospective phase II drug trial to assess the safety and efficacy of (+)-EPI in the treatment of Friedreich’s Ataxia. Subjects will be evaluated at outpatient clinic visit appointments and interested qualified subjects will be consented and offered participation in this trial. Once consent has been obtained, baseline values will be established and subjects will begin treatment and follow-up over a 24 week period. Clinical and biochemical parameters will be assessed at baseline and at 12 and 24 weeks after initiation of treatment.
Overall Study Duration	Two years estimated to complete enrollment
Subject Participation Duration	24 weeks
Single or Multi-Site	Single center
Objectives	
Primary: To assess the safety and clinical efficacy from neurological, cardiac and metabolic evaluations of patients before and after treatment.
 
Secondary: To assess (i) up-regulation of relevant mitochondrial proteins (frataxin and ETC complexes I-V) and (ii) reduction of urine F2-isoprostane, before and after treatment.
 
Exploratory: To assess myocardial oxygenation by Blood Oxygenation Level Dependent (BOLD) sequence cardiac MRI, and myocardial perfusion index by Regadenoson-stress-perfusion cardiac MRI, before and after treatment as non-invasive, more sensitive endpoints for future studies.
 
To investigate neuroimaging biomarkers of disease progression including spinal cord and cerebellar volumetry, Diffusion Tensor Imaging (DTI), and Magnetic Resonance Spectroscopy (MRS).

Number of Subjects	10 subjects

Diagnosis and Main Inclusion Criteria	Study participants between the ages of ≥ 10 and ≤ 50 must have a confirmed diagnosis of Friedreich's Ataxia with disease duration ≤ 7 years and at least one affected organ system (cardiac or neurological)
Study Product, Dose, Route, Regimen	(+)-Epicatechin 25mg capsules will be administered orally TID for 24 weeks, with dose escalation to 50mg TID at 3 months for subjects not showing improvement.
Duration of Administration	24 weeks
Reference therapy	No reference therapy
Statistical Methodology	With a sample size of 10 patients we should have 80% power to detect an effect size of 1 standard deviations or larger on outcome measures

1 Introduction

This document is a protocol for a human research study. This study will be carried out in accordance with this protocol and the applicable United States government regulations including Food and Drug Regulations 21 CFR Part 50 (Human Subject Protections), Part 54 (Financial Disclosure of Clinical Investigators), Part 56 (Institutional Review Boards), Part 312 (IND) and Good Clinical Practice guidelines, as well as the applicable Mayo Clinic research policies and procedures.

1.1 Background

Mitochondrial disease (MtD) includes a large number of human disorders with a collective prevalence of 10-15 cases per 100,000, resulting from functional defects in the mitochondrial electron transport chain (ETC). ETC defects impair the production of ATP and also enhance the generation of reactive oxygen species (ROS), leading to the combination of energy deficit and oxidative damage underlying the pathogenesis of MtD. Given the vital role played by the ETC in mammalian cells, ETC defects may affect virtually any tissue or organ system and present with a wide variety of symptoms in both children and adults. Progressive multisystem involvement occurs in most patients with variable combinations of neurological, muscular, cardiac, metabolic and other deficits [1]. The clinical complexity of MtD is associated with equally significant genetic complexity owing to the fact that a large number of both mitochondrial and nuclear genes are required for the biogenesis and function of the ETC. Indeed, while ETC defects were originally linked to mutations in mitochondrial genes, over 30 nuclear genes were subsequently implicated and more are being identified. Mutations in nuclear genes can cause MtD via a broad spectrum of molecular mechanisms that may affect the integrity of the mitochondrial genome, the assembly of specific ETC complexes, and the synthesis or delivery of metal or Fe-S cofactors needed for ETC activity [1].

Research Idea: While many recent advancements in genetic and biochemical testing facilitate the diagnosis of MtD, there is no effective therapy available for this group of disorders as a whole [2]. In light of the common underlying pathogenic mechanism of energy deficit and oxidative damage, we hypothesize that the induction of mitochondrial biogenesis and bioenergetics along with simultaneous up-regulation of the cellular antioxidant defenses is a strategy capable to ameliorate MtD. To test this hypothesis we propose to conduct a phase II drug clinical trial to test the efficacy of a pharmaceutical grade synthetically-produced form of Epicatechin (EPI) in patients with Friedreich's Ataxia.

The active compound (-) EPI is found in cocoa powder, green tea and other plants [13]. Recent research has indicated that its enantiomer, (+)-EPI is more potent and more efficacious in vitro and in vivo compared to (-)-EPI with respect to stimulating new mitochondrial formation. (+)-EPI is also a natural product, found in the guarana berry that serves as the source of widely consumed beverages in South America [14]. Guarana is generally recognized as safe and a permitted food additive by FDA [15]. (+)-EPI is not commercially available in current Good Manufacturing Practices (cGMP) grade monomeric form, for any purpose, research or otherwise. Cardero Therapeutics has developed the first scalable manufacturing process that provides pharmaceutical grade (+)-EPI. This manufacturing process has already been accepted by the FDA in the context of a previously filed IND for determining the tolerability and PK profile of (+)-EPI in healthy human volunteers. Given the severity of FA, we propose studying the effects of the more potent enantiomer of epicatechin. In addition, EPI can be administered orally, readily crosses the blood-brain barrier, and is generally recognized as a safe compound [9, 12].

Why FA? FA is a paradigm for MtD in which intronic trinucleotide repeat expansions in the FA gene lead to depletion of the mitochondrial protein frataxin [16]. Frataxin is an essential iron chaperone required for Fe-S cluster assembly, and a reduction in the levels of frataxin leads to ETC dysfunction, energy deficit and oxidative damage via iron-catalyzed Fenton chemistry [17]. FA patients develop progressive neuro-degenerative disease often associated with cardiomyopathy, diabetes mellitus, and muscle weakness with a median age of onset of 10 years. Thus, we believe EPI is a promising compound for the treatment of FA given its unique biological effects that appear likely to be able to counteract the pathophysiology of FA and thereby slow down or stop disease progression.

Therefore, the ability of Epicatechin to reverse oxidative injury, ameliorate congestive heart failure, and induce mitochondrial repletion, coupled with its safety as a dietary product, argues for investigating its therapeutic qualities in patients with FA. Moreover, Cardero Therapeutics have

teamed-up with our multi-disciplinary FA group of clinicians and scientists who share a long interest in MtD and FA at Mayo Clinic, enabling this initial pilot study and future larger studies.

1.2 Investigational Agent

Description:

Cardero Therapeutics has synthesized pharmaceutical grade (+) Epicatechin, a more active natural product enantiomer of epicatechin, which is otherwise not available in a purified form. EPI is associated with signaling mechanism that induces mitochondrial biogenesis via activation of the transcription factor PGC-1 α [9], upregulates endogenous antioxidant mechanisms (SOD2, catalase) controlled by the Nrf2 (nuclear factor-E2-related factor-2) pathway [18], promotes fatty acid oxidation through regulation of SIRT3 (Sirtuin 3) signaling [9, 19] and enhances insulin sensitivity through the PI3K/AKT (Phosphoinositide 3-kinase/ Protein kinase B) pathway and AMPK [10] which may further improve metabolic dysfunction in FA.

Pharmacology:

Pharmacokinetics of both isoforms of EPI have been described in a previous IND filed by [name] (IND 122158), by Barnett et al, 2015, and Ottaviani et al, 2011 [20, 21]. Numerous publications indicate the polyphenol epicatechin does not undergo Phase I hepatic metabolism mediated by cytochrome P450 oxidases. In the liver, (-)-EPI undergoes modification (by uridine-5-diphosphate glucuronosyl-transferases, sulfo-transferases, and catechon-O-methyltransferases), which results in glucuronide, sulfate, or methyl conjugates/metabolites, accounting for more than 85% of the absorbed epicatechin. Tmax ranges from 3.2-3.8 hours and T1/2 ranges from 1.8.-3.8 hours. Virtually no unconjugated epicatechin is observed after 1 hour. Bioavailability is approximately 30%. (+)-EPI demonstrates moderately less bioavailability and less conjugation with glucuronide or sulfate compared to (-) EPI [21, 22]. It is less effective as an inducer of NO synthesis in vitro and in vivo. The half-life is less than 90 minutes for both enantiomers [21]. In addition, (+)-EPI has no inhibitory effect on the five most important P450 oxidases in a hepatic microsome assay [23]. In vitro, (+)-Epicatechin demonstrates, no Human Ether-a-Go-go Related Gene (HERG) activity [24] and no non-selective interactions with a diverse panel of receptors and enzymes [25].

1.3 Preclinical Data

Effect of (-)-EPI on mitochondrial biogenesis in skeletal muscle and in patients with Diabetes and heart failure. Emerging rodent and human data confirm that (-)-EPI increases mitochondrial biogenesis and the expression of mitochondrial electron transport chain complex proteins by up regulating AMPK, SIRT1 and PGC1-alpha [3, 6, 11, 20, 26-28]. Thus (-)-EPI stimulates muscle mitochondrial mass/volume and increases maximal mitochondrial respiratory rate. In addition, (-)-EPI promotes the ability of muscle to regenerate by upregulating muscle growth promoters (optimizing follistatin/myostatin ratio) [6]. These changes have been documented in the skeletal muscle (SkM), heart, and liver and are accompanied by improvements in exercise performance and congestive heart failure.

(-)-EPI ameliorates oxidative stress and improves cardiac function. In a mouse model (-)-EPI treatment resulted in improved oxidative stress evidenced by recovery of key elements of redox

balance (glutathione/oxidized glutathione ratio, thioredoxin) and enhanced endogenous anti-oxidant enzymes (superoxide dismutase 2, catalase and citrate synthase) [5]. Furthermore, the investigators found decreases in heart and skeletal muscle fibrosis, accompanied by an improvement in muscle function. In a rat model of non-dystrophic heart failure oral administration of (-)-EPI effectively suppressed abdominal aorta ligation-induced CHF [29]. In addition, (-)-EPI demonstrated preservation of myocardial structure and function in a model of chronic heart failure [30].

EPI appears to act as an exercise mimetic [31], based on its positive effects on cardiovascular disease and type 2 diabetes associated with the consumption of EPI-rich foods [13]; and the positive effects of purified EPI on mitochondrial biogenesis and oxidative stress [27], metabolism [13], and skeletal muscle growth and differentiation [32].

EPI is a neuroprotectant and inducer of neural regeneration. Neuronal injury as a result of mitochondrial dysfunction is a component of the pathophysiology of Friedreich's ataxia. There is evidence for direct effects of epicatechin in preserving neurons. Wild-type mice pretreated orally with epicatechin before middle cerebral artery occlusion (MCAO) had significantly smaller brain infarcts and improved neurologic deficit scores (NDS) than did a vehicle-treated group [33].

In a medium throughput screen for neuroprotective compounds using primary mixed neuronal cells and a mitochondrial toxin, epicatechin was discovered to be a potent direct neuroprotectant. It effectively decreased intracellular oxidative stress and normalized the signaling pathway of brain-derived neurotrophic factor (BDNF) [12].

Cell viability assays with neuronal cultures further confirmed that epicatechin can directly protect neurons against oxidative insults. With particular relevance to FA, much of the neuronal benefit appeared to be due to the induction of endogenous anti-oxidant mechanisms controlled by the Nrf2 pathway [18].

Effects of (+)-Epicatechin in Normal Mice. Studies have been performed to evaluate effects on exercise capacity using wild type mice treated with either water (control), (-)-epicatechin (1 mg/kg/day) or (+)-epicatechin (0.1, 0.3 or 1 mg/kg/day). Endpoints evaluated include the mitochondrial biogenesis transcription factors AMPK and PGC1- α . (Figure 2) Results indicate that following 2 weeks of treatment, (+)-epicatechin could enhance exercise capacity (as assessed by treadmill testing, (Figure 3) in a magnitude similar to 1 mg/kg/day of (-)-epicatechin but at lower doses (equivalency noted at 0.3 mg/kg/day). Biochemical analyses (Western blots) of muscle samples from the above mice demonstrated a similar pattern of responses, whereby (+)-epicatechin was as effective at lower doses or more effective at comparable doses when probing for effects on recognized key modulators of metabolism.

Figure 2

[figure not shown]
[figure not shown]

Figure 3

1.5 Dose Rationale and Risk/Benefits

For this study, (+)-EPI will be administered orally at a starting dose of 75 mg total daily dose (25 mg TID) escalated to 150mg total daily dose (50 mg TID) for those subjects not showing improvement at 12 weeks. (+)-EPI plasma levels will be measured before and after 3 (+/-1), 12 (+/-1), and 24 (+/-1) weeks of treatment to assess study drug dosing compliance.

The dosage is supported by 3 factors:

- 1) Human efficacy has been demonstrated with (-) Epicatechin at 1.0-1.5 mg/kg [4, 20, 34] given at 50 mg twice a day for up to 8 weeks. The twice a day dosing was chosen because once a day dosing did not demonstrate efficacy, presumably because of the short half-life (Barnett et al,2015)
- 2) At 1 mg/kg in animals, (+)-Epicatechin is more effective in stimulating exercise endurance and activating muscle AMPK and PGC1alpha than (-) –Epicatechin. (Figure 2, Figure 3)
- 3) Because epicatechin is not subject to Phase 1 hepatic metabolism, the pharmacokinetics in rats is similar to that of humans and the effective dosage in rodents predicts effective dosage in humans [4, 26]. FA patients will range between 25-70 kg in weight. Therefore, we will be well within the in vivo documented range of efficacy in rodent models and within the safe administration of (+)-EPI in previously published pharmacokinetic studies [21].

2 Study Objectives

See Section 3 for detailed descriptions of outcomes measures/endpoints.

Primary Objective(s):

To assess the clinical safety and efficacy of (+)-EPI in the treatment of Friedreich's Ataxia, based on changes from baseline in neurological and cardiac function, following dosing with (+)- EPI.

Secondary Objective(s):

To assess changes from baseline following treatment with (+)-EPI.

- Metabolic status relating to diabetes

- Mitochondrial function

Exploratory Objective(s):

To assess changes from baseline following treatment with (+)-EPI in:

- Myocardial oxygenation and myocardial perfusion, as possible non-invasive, more sensitive endpoints for future studies
- Muscle regeneration as measured by (serum) biomarkers follistatin and myostatin

3 Study Design and Visit Description

See also the Protocol Schedule of Events in Appendix II.

Visit 1: Baseline- Week 0

At the baseline visit, the study team will review participant eligibility. For participants who meet inclusion criteria, an informed consent discussion will take place with subject and LAR, when applicable. Adequate time will be provided for the subject/LAR to read the consent and have any and all questions answered prior to signing the consent form. Study staff will complete a review of medical history and concomitant medications, conduct a physical exam and including neurological assessment with a FARS scoring for enrolled subjects. A 3 month supply of (+)- EPI will be dispensed to the subjects/LAR along with a dosing/adverse event diary to be completed by the subject and/or LAR. The diary entries will be reviewed with participants during subsequent clinic visits. All study tests will be conducted at Mayo Clinic, with the exception of study drug levels and follistatin/myostatin analysis, to be conducted by a research laboratory at UC-San Diego. The following evaluations will be completed:

- Physical Examination, Vitals, Blood Pressure
- Drug level analysis of (+)- EPI in blood
- Follistatin/myostatin analysis in blood
- Friedreich's Ataxia Rating Scale (FARS) Assessment (See Attachment I)
- Urine analysis
 - F2-isoprostane (8-iso prostaglandin F2, an eicosanoid produced by oxidation of tissue phospholipids) to assess for oxidative stress
- Blood chemistry
 - Serum BNP, calcium, cardiac troponin I, CBC, creatinine with eGFR, frataxin, glucose tolerance test, hemoglobin A1C, iron, mitochondrial complex I-V levels, potassium, PT/PTT, sodium, ST2, triglycerides, ALT, AST, Alkaline Phosphatase and ceruloplasmin [35].
- Neurology studies
 - Cerebellar and spinal cord MRI with volumetry, DTI, and MRS analysis
- Echocardiogram and electrocardiogram
- Cardiac MRI with BOLD/Perfusion analysis
- Urine pregnancy test for female subjects
- We may collect blood for off study evaluation if budget allows

- Respiratory chain function, aconitase, catalase, PGC1 α , SOD2 in blood

Week 3 (+/- 1 week): Venipuncture- No onsite visit to Mayo Clinic required

A test kit will be mailed or provided at visit 1 by to the participant for venipuncture blood collection by a local physician. The sample shipment will be pre-addressed to the laboratory at UC-San Diego. Test results will subsequently be provided to the PI and maintained with study documents for:

- Drug level analysis of (+)- EPI in blood
- Follistatin/myostatin level in blood

Telephone calls between baseline and 3 month on-site visits: The subjects/LAR will be contacted by study staff approximately every 15 days to assess progress, symptoms and dosing compliance. If it appears subject is experiencing adverse changes and the Investigator feels an on-site visit is warranted, the subject will be asked to come in for an interim clinic visit.

Visit 2: Week 12 (+/- 1 week)

At Visit 2, the participant will undergo a physical exam and FARS scoring. Medical history, changes to concurrent medications, adverse event diary and dosing will be reviewed and additional diaries dispensed, as needed. A physical examination will be conducted. Dosing of (+)- EPI will be adjusted depending on the performance of the 8m timed walk completed through the FARS assessment and/or cardiac assessment via MRI. If the participant shows improvement (as defined in section 3.1) compared to baseline in composite score, including the 8m timed walk or cardiac function by MRI, the medication dosage will remain the same. If the participant shows no improvement or worsening compared to baseline, the (+)- EPI dose will be increased. Additional investigations include:

- Physical Examination, Vitals, Blood Pressure
- Drug level analysis of (+)- EPI in blood
- FARS Assessment
- Blood chemistry
 - Serum BNP, calcium, cardiac troponin I, CBC, ceruloplasmin, creatinine with eGFR, frataxin, , hemoglobin A1C, iron, mitochondrial complex I-V, potassium, PT/PTT, sodium, and ST2, triglycerides, and liver panel (ALT, AST, and Alkaline Phosphatase)
- Cardiac MRI with BOLD
- Urine pregnancy test

Telephone calls between 3 month and 6 month on-site visits: The subjects/LAR will be contacted by study staff approximately every 15 days to assess progress, symptoms and dosing compliance. If it appears subject is experiencing adverse changes and the Investigator feels an on-site visit is warranted, the subject will be asked to come in for an interim clinic visit.

Visit 3: Final Evaluation- Week 24 (+/- 1 week)

At the final visit, the participant will undergo a physical exam and neurological/cardiac assessments. Changes in symptoms and any concurrent medications will be assessed and the dosing/adverse event diary will be reviewed and collected/retained. Final investigations include:

- Physical Examination, Vitals, Blood Pressure FARS Assessment
- Urine analysis: F2-isoprostane
- Blood sample(s)
 - Analysis of (+)- EPI drug level and follistatin/myostatin levels
- BNP, Calcium, cardiac troponin I, CBC, ceruloplasmin, creatinine with eGFR, frataxin, glucose tolerance test, hemoglobin A1C, iron, mitochondrial complex I-V, potassium, PT/PTT, sodium, ST2, triglycerides, and liver panel (ALT, AST, and Alkaline Phosphatase) Neurology studies
 - Cerebellar MRI conducted on a non-FDA approved compact 3T MRI scanner and associated software and spinal cord MRI with volumetry, DTI, and Magnetic Resonance Spectroscopy (MRS) analysis
- Echocardiogram and electrocardiogram
- Cardiac MRI with BOLD/Perfusion analysis
- Urine pregnancy test for female subjects
- We may collect blood for off study evaluation if budget allows
 - Respiratory chain function, aconitase, catalase, PGC1 α , SOD2 in blood

3.1 General Design

This is an open label, single center, and prospective phase II drug trial to assess the safety and efficacy of (+)-EPI in the treatment of Friedreich's ataxia. Duration of the trial including recruitment and final assessment is estimated at approximately 2 years: start date early 2016 to approximately late 2017, depending upon recruitment rate. Subjects will be evaluated at outpatient clinic visit appointments and interested qualified subjects will be consented and offered participation in this trial. Once consent has been obtained, baseline values will be established and subjects will begin treatment and follow-up over a 24 week period. Clinical and biochemical parameters shown in Table 1 will be assessed in each patient at baseline and at 3, 12 and 24 weeks after initiation of treatment. See Protocol Schedule of Events in Attachment II.

Subjects will be dispensed bottles of 25mg capsules of open-label (+) EPI with instructions for oral TID dosing to be taken on an outpatient basis. All subjects will start at 75 mg total daily dose. Those subjects showing improvement at 12 weeks as defined below, will continue at the starting dose level of 75 mg total daily dose (one, 25mg cap TID) to 24 weeks. Subjects showing no improvement or worsening at 12 weeks will have their dose escalated as described below for the remainder of the study, as tolerated.

Dose Escalation at 12 weeks: Those subjects showing no improvement or worsening in the 8 meter timed walk/FARS composite score or with no improvement in cardiac function by MRI at the 12-week clinical assessment, as compared to baseline, will have their dose increased at the 12 week visit to 150 mg total daily dose (two, 25mg caps TID) until 24 weeks, as tolerated.

Neurological Status Improvement Definition: If there is no change or the timed walk is longer at 12 weeks than at the baseline walk time or the FARs composite score has not changed or has

increased, as compared to baseline FARS composite score, this will be considered no improvement/worsening of neurological status. Improvement is defined as a greater than 1 point decrease in the FARS composite score, as compared to the baseline composite score [36].

Cardiac Status Improvement Definition: If the cardiac function is the same as baseline or worse at 12 weeks, this will be considered no improvement /worsening of cardiac LV structure/function.

Improvement in left ventricular structure and function by MRI is defined as any one of the following:

1. If LV mass was abnormally increased at baseline, reduction in LV mass of > 10% from baseline or
2. If LV ejection fraction was reduced at baseline, increase in LV ejection fraction of > 5% from baseline or
3. If LV end-diastolic volume was abnormally increased at baseline, reduction in LV end-diastolic volume of > 10% from baseline.

Neurologic Status: If spinal cord and cerebellar volumes (based on 3D volumetric MRI), fractional anisotropy (based on DTI), and metabolites (based on 3D MRS) are worse at 24 weeks compared to baseline, this will be considered no improvement /worsening of neurologic structure/function.

Worsening in neurologic structure and function by MRI is defined as any one of the following:

1. If spinal cord volumes were abnormally decreased at 24 weeks compared to baseline, reduction in cord volume of > 10% from baseline or
2. If cerebellar volumes were abnormally decreased at 24 weeks compared to baseline, reduction in cerebellar volume of > 10% from baseline or
3. If spinal cord fractional anisotropy was abnormally decreased at 24 weeks compared to baseline, reduction in fractional anisotropy of > 10% from baseline or
4. If cerebellar metabolite ratios (NAA/Cr, Cho/Cr, NAA/Cho) change > 5% from baseline at 24 weeks.

Study drug will be dispensed at the baseline visit for 12 (+2) weeks of dosing initially and resupplied at the 12 week visit for an additional 12 (+2) weeks of dosing at either the starting dose or escalated dose following re-assessment for changes in neurological and cardiac functions as described above.

Table 1

Neuromuscular	Cardiac	Metabolic & Biochemical
FARS (disability, ataxia, fine motor skills, peripheral neuropathy, and gait)	MRI (left ventricular mass, end-diastolic and end-systolic volumes, ejection fraction, strain analysis, myocardial fibrosis)	Glucose tolerance test
Brain MRI (spinal cord and cerebellar volumetry, DTI, and MRS)	Blood Oxygenation Level Dependent (BOLD) MRI (myocardial oxygenation)	Whole Blood Hemoglobin A1C Frataxin

		Heart Failure Biomarkers (BNP, and others) triglycerides
Magnetic Resonance Spectroscopy (lactate, N-acetylaspartate, and choline)	Regadenoson-stress-perfusion MRI (myocardial perfusion index)	Leukocytes ETC Complexes Other relevant proteins Bioenergetics
	M-mode, 2D, 3D, tissue Doppler (left ventricular mass, volumes, systolic and diastolic function)	Urine F2-isoprostane
	Echocardiography (strain imaging)	

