Attachment II
Protocol Schedule of Event

^a (+)-EPI drug levels and follistatin/myostatin levels will be analyzed by UC-San Diego. All other laboratory analyses will be conducted by Mayo Clinic Department of Lab Medicine and Pathology and Research Laboratories

15-006845 Protocol Schedule of Events						
Study Activity	Week 0 Baseline Clinic Visit	Interim Contacts	Week 3 (+/- 1 week) Lab Only	Week 12 (+/- 1 week) Clinic Visit	Interim Contacts	Week 24 (+/- 1 week) Clinic Visit
Visit	1			2		3
Review Eligibility	X					
Informed Consent	X					
Medical History	X			X		X
Concurrent Medications	X			X		X
Physical Exam/Vitals/BP	X			X		X
Drug Level (+)- EPI ^a	X		X	X		X
Follistatin/Myostatin ^a	X		X			X
Blood labs ^b	X			X		X
Urine Analysis ^c	X					X
Neuro Studies ^d	X					X
Cardiac MRI/BOLD	X			X		X
Echo/ECG/Perfusion MRI	X					X
FARS Assessment	X			X		X
Urine Pregnancy Test ^e	X			X		X
Dispense Study Med Dosing/AE Diary ^f	X			X		
Increase Dose, if appl ^g				X		
Review Dosing and AE diary				X		X (collect)
Interim Contacts ^h		X			X	
Off-study evaluation ⁱ	X					X

^a (+)-EPI drug levels and follistatin/myostatin levels will be analyzed by UC-San Diego. All other laboratory analyses will be conducted by Mayo Clinic Department of Lab Medicine and Pathology and Research Laboratories

^b: Serum BNP, Calcium, cardiac troponin I, Complete Blood Count (includes RBCs, WBCs with differential, platelets), ceruloplasmin, creatinine with eGFR, frataxin, glucose tolerance test (not performed week 12), hemoglobin A1C, iron, mitochondrial complex I-V, potassium, PT/PTT, sodium, ST2, triglycerides, liver enzymes (AST, ALT, Alk phos)

^c: F2-isoprostane

^d: Magnetic resonance imaging of cerebellum and spinal cord, magnetic resonance spectroscopy

^e: Urine pregnancy test (females of childbearing potential)

^f: (+)- EPI orally administered daily for 24 weeks

^g: (+)-EPI dose will be increased from 75mg/day to 150mg/day, if 8m timed walk via FARS assessment or cardiac evaluation shows no improvement or worsens

^h: Study site staff will contact the subject/LAR approximately every 15 days between the Baseline, Week 12 and Week 24 visits to assess clinical changes, adverse events and dosing compliance.

ⁱ. Respiratory chain function, aconitase, catalase, PGC1 α , SOD2 in blood if needed

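### The week-12 dose rule contradicts itself: a subject who improves in only one domain stays at 75 mg/day under Visit 2 but goes to 150 mg/day under Section 3.1 and footnote g

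*Combined protocol and SAP*

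**What the plan says.** Three places in the combined protocol and SAP tell staff what to do with the dose at week 12.

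- **Section 3, Visit 2.** The dose is to depend on "the performance of the 8m timed walk completed through the FARS assessment and/or cardiac assessment via MRI". For a participant who improves from baseline in "composite score, including the 8m timed walk or cardiac function by MRI, the medication dosage will remain the same". Otherwise the dose goes up.
- **Section 3.1, dose escalation sentence.** The dose rises to 150 mg/day for subjects with "no improvement or worsening in the 8 meter timed walk/FARS composite score or with no improvement in cardiac function by MRI".
- **Attachment II, footnote g.** The dose rises "if 8m timed walk via FARS assessment or cardiac evaluation shows no improvement or worsens".

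Three other places mention the rule without saying whether one domain or both must improve. Section 3.1 begins: "Those subjects showing improvement at 12 weeks as defined below, will continue at the starting dose level". The Study Summary describes the regimen "with dose escalation to 50mg TID at 3 months for subjects not showing improvement". Section 1.5 escalates "for those subjects not showing improvement at 12 weeks".

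Section 3.1 defines each domain separately. Neurological improvement is a FARS composite fall of more than 1 point; a longer walk, or a composite that is unchanged or higher, counts as no improvement or worsening. Cardiac improvement is any one of three MRI criteria, the first being "If LV mass was abnormally increased at baseline, reduction in LV mass of > 10% from baseline". The other two, for ejection fraction and end-diastolic volume, are likewise conditional on an abnormal baseline value. Section 4.1 requires only one affected system, cardiac or neurological.

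**The concern.** Visit 2 joins the domains so that one improvement is enough to stay on the starting dose. Section 3.1 and footnote g join them so that one failure is enough to escalate. These rules differ for exactly the subjects with a mixed result, and no text gives precedence. Visit 2 refers to Section 3.1 for what improvement means, but Section 3.1 never says how to combine the two definitions.

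At stake is a twofold dose difference for the second half of treatment. Two subjects with identical week-12 findings could be treated differently, each in line with the protocol. Week-24 results would then rest on a dose that depended on which paragraph was followed.

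**Working it through.** **1. The plan's own figures.** The Section 5.2 dispensing table reproduces. Each period covers 12 + 2 weeks = 98 days. At three capsules a day, 3 × 98 = 294 capsules (7 × 42). At six a day, 6 × 98 = 588 (14 × 42). Totals are 294 + 294 = 588 and 294 + 588 = 882, a ratio of 1.50. The Section 7.1 power also reproduces: a paired t-test with n = 10, effect size 1, two-sided 5%, 9 degrees of freedom and noncentrality √10 gives 0.803 against the stated 80%. The dose rule does not enter that calculation.

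**2. The rules as logic.** Let N be neurological improvement and C cardiac improvement.

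- Visit 2: stay if N or C.
- Section 3.1 escalation sentence: escalate if not-N or not-C, so stay only if N and C.
- Footnote g: the same form as Section 3.1, with the timed walk standing for N. The table assumes that walk and FARS agree.

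| N | C | Visit 2 | Section 3.1 | Footnote g |
|---|---|---|---|---|
| yes | yes | 75 | 75 | 75 |
| yes | no | 75 | 150 | 150 |
| no | yes | 75 | 150 | 150 |
| no | no | 150 | 150 | 150 |

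Doses are mg/day. The conflict is confined to the two mixed rows.

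**3. Size for one mixed-result subject**, excluding the dispensing overage.

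- Weeks 12 to 24 (84 days): 75 × 84 = 6,300 mg, or 150 × 84 = 12,600 mg.
- All 24 weeks: 6,300 + 6,300 = 12,600 mg, or 6,300 + 12,600 = 18,900 mg. Ratio 18,900 / 12,600 = 1.50.

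**4. Subjects with normal LV values.** C can be true only if LV mass, ejection fraction or end-diastolic volume was abnormal at baseline. If none was, C is false by definition. The literal Section 3.1 sentence then gives 150 mg/day whatever N is, while Visit 2 lets N decide. Because Section 4.1 asks for only one affected system, such subjects are eligible.

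**5. FARS against the walk.** Take a FARS composite fall of more than 1 point with a walk longer than at baseline. The fall meets the definition of improvement; the longer walk meets the definition of no improvement. Both apply, and nothing ranks them. This needs only that the composite is not the walk alone, so that other items can outweigh it.

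**6. What the dose reaches.** Section 3.2 lists six primary efficacy endpoints: FARS, cord fractional anisotropy, cardiac MRI, echocardiogram, ECG and biomarkers. Three of them (fractional anisotropy, echocardiogram, ECG) are read only at week 24, after the dose decision.

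**The case against.** The best defence is that the Section 3.1 sentence was meant loosely, as no improvement in either domain. The Study Summary, Section 1.5 and the opening of Section 3.1 treat improvement as a single patient-level state, and on that reading Section 3.1 agrees with Visit 2. This has some force, but the sentence repeats its negative before the cardiac part, and footnote g separately escalates on either failure. The literal reading is the more natural one, and the fact that two readings are possible is itself the problem.

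Two further points stand. Two of the three operative statements favour the stricter rule, so Visit 2 may be the slip and the sponsor must choose. Also, at a single centre where a study investigator writes each prescription, one reading may in practice be applied throughout; the document does not ensure it.

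A reader might infer more than the text supports:

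- **That the efficacy analysis fails or loses power.** It does not. Week-12 measurements precede the decision, and Section 7.2 plans paired changes pooled over doses.
- **That small FARS falls fit no definition.** Improvement is defined as a fall of more than 1 point, so a smaller fall is already not improvement. Arguments from score increments or a scale floor would need the composite to be the 0 to 159 total, whereas Visit 2 describes it as including the timed walk.
- **That non-walkers have no neurological criterion.** Footnote g names only the walk, but Section 3.1 names the FARS composite as well.
- **That the adverse-event comparison between treatment groups in Section 3.5 is compromised.** This single-arm plan never defines those groups, so nothing can be rested on the phrase.

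**Conclusion.** The contradiction is real and lies in an operative dosing instruction. On the literal wording, a subject improving in exactly one domain has two protocol doses for weeks 12 to 24, a 24-week total of 12.6 g or 18.9 g. The literal Section 3.1 rule also escalates every subject with normal baseline LV mass, ejection fraction and end-diastolic volume, regardless of neurological gain. The overlap between the FARS and walk definitions is a second, smaller defect.

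The conclusion rests on the literal reading of Section 3.1 and footnote g and on no assumed rate. The documents give no response rates or baseline LV distribution, so the number affected cannot be derived; it could be anywhere from 0 to 10 of 10. The issue should be fixed because it decides a child's or adult's dose and the exposure behind the week-24 results. It does not threaten the trial as a whole.

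**What to change.** Put one identical rule in Visit 2, Section 3.1 and footnote g. Suggested content:

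1. Stay at 75 mg/day if either assessable domain improves; otherwise escalate to 150 mg/day as tolerated.
2. Treat the cardiac domain as not assessable when none of the three LV values was abnormal at baseline. The neurological criterion alone then decides.
3. State which measure governs when FARS and the timed walk disagree, or when there is no walk time. The FARS fall of more than 1 point is the natural choice, being the only positive definition of neurological improvement given.

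If the sponsor intends escalation unless both domains improve, say so in all three places and still exempt a cardiac domain that cannot be assessed.

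The cost is a protocol amendment, with no added subjects or procedures. Item 3 is more than editing, since it stops a slower walk from triggering escalation when FARS has improved; the sponsor should adopt it deliberately. Under the suggested rule fewer subjects reach 150 mg/day than under the literal Section 3.1 sentence, so less is learned about that dose.
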